Our study will enroll participants with at least two fingernails involved. This will allow us to use placebo in one fingernail of every participant, thus establishing the efficacy of ITA in our study by allowing us to compare placebo to ITA. In addition to efficacy assessments, we will measure changes in quality of life due to the study intervention as an outcome. Quality of life assessments will be done with the NPQ10 assessment, which is a validated assessment tool developed to measure quality of life in nail psoriasis.[14] This tool is included in Appendix B.

All fingernails not treated with placebo will undergo randomization to four groups corresponding to four concentrations of ITA under investigation (2.5, 5.0, 7.5, 10.0 mg/mL). Thus, a participant with five affected fingernails may have a different concentration of ITA used as the study intervention in each fingernail. This approach has been used in studies of ITA in other dermatologic diseases such as alopecia areata. [15] In the cited study, the lesions of subjects with alopecia areata were divided into four quadrants, corresponding to four concentrations of ITA that were injected. We believe this approach will be helpful in comparing the efficacy of different concentrations in the same patient.

SIGNIFICANCE

Psoriasis is a chronic, inflammatory condition that affects millions of people in the United States. Approximately 50% of patients with cutaneous psoriasis have nail involvement; nail psoriasis causes significant pain, and can lead to loss of manual dexterity, therefore impairing the ability to use the hands or perform work. Intralesional triamcinolone acetonide is considered one of the mainstays of treatment for nail psoriasis. By determining the lowest effective concentration of this medication for nail psoriasis, we can minimize side effects for millions of people affected with nail psoriasis worldwide.

OBJECTIVES

The primary objective of this study is to determine the lowest effective concentration of intralesional triamcinolone acetonide in the treatment of nail psoriasis.

The secondary objective is to determine that intralesional triamcinolone acetonide is effective in the treatment of nail psoriasis when compared to placebo, using the Nail Psoriasis Severity Index as a measure of improvement.

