Another secondary objective is to determine the rate and nature of side effects experienced by patients using different concentrations of intralesional triamcinolone acetonide for the treatment of nail psoriasis.

Another secondary objective is to assess baseline quality of life in patients with nail psoriasis and determine if there is a change in quality of life with the study intervention.

SUBJECT POPULATION

Inclusion Criteria:

The subject must meet ALL the criteria listed below for entry:

1. Subject must be at least 18 years of age, of either sex or transgendered individuals, and of any race;
2. Subject must have nail psoriasis that is clinically diagnosed of at least 2 fingernails.
3. Subject must be willing to give written informed consent and able to adhere to procedures and visit schedules;
4. Subject must consent to having the fingernails photographed during the study period

Exclusion Criteria:

The subject will be excluded from entry if ANY of the criteria listed below are met:

1. Subject with any clinically significant condition or situation, other than the condition being studied that, in the opinion of the investigator, would interfere with study evaluations or optimal participation in the study. This is including, but not limited to: immunodeficiency, onychomycosis, any other nail condition other than psoriasis, allergy to triamcinolone acetonide, local anesthetic, normal saline, or any other material used for procedures.
2. Subject who has received radiation therapy, chemotherapy, and/or immunosuppressive drugs within 6 months of study, and/or oral corticosteroids for >1 month within the 6 months of study (exception: inhaled steroids);
3. Subject known to have received treatment with investigational drugs or devices within 30 days prior to enrollment into this study;
4. Subject who is unwilling to abstain from any cosmetic nail treatments outside those provided by the study clinic, beyond basic nail trimming (i.e. no spa nail treatments, no nail polish use, no other topical prescription nail medication);

5. Subject who is unwilling to abstain from any medical nail treatments on their nails other than the study intervention (i.e. topical steroids, antifungal creams) for the duration of the study intervention and for duration of the washout period (if applicable);
6. Subject who is part of the staff personnel directly involved with this study or a family member of the investigational study staff

CONCOMITANT MEDICATIONS

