All concomitant medication usage from the period of 60 days prior to the trial through the trial period shall be documented and include the following information:

1. Medication
2. Indication
3. Dosage (including frequency)
4. Start / Stop date

All concomitant medication usage will be checked with respect to exclusion criteria and cross-referenced to adverse events (if any).

RESEARCH DESIGN / METHODS

Our approach is to assess the efficacy and safety of different concentrations of ITA in the treatment of nail psoriasis. A similar approach has been taken with psoriasis of the skin, and alopecia areata.[15, 16]

Hypothesis: The lowest concentration of ITA tested offers the best ratio of efficacy to safety.

Study Design: A total of 10 subjects who have nail psoriasis of at least two fingernails will be enrolled. During the screening visit, the investigator will discuss with each subject the nature of the study, its requirements and its restrictions during the Informed Consent Process.

The following will be performed at the screening visit:

- Review of inclusion/exclusion criteria
- Medical history and demographics including age, gender, history of psoriasis
- Review of medications
- Examination of the fingernails
- Possible tissue sampling (clipping the nail) to rule out onychomycosis
- X-ray of the affected hand
- Administration of a survey assessing quality of life at baseline.
- Use the study intervention (intralesional triamcinolone acetonide injections) on your fingernail(s)

Eliciting the patient history and physical exam are part of standard clinical practice.

Nail psoriasis is a clinical diagnosis. Tissue sampling may be taken if there is a question about diagnosis, or if there is a possible confounding diagnosis such as onychomycosis. X-rays of the hand may also be taken to determine if there is co-existing arthritic involvement, which is very common in nail psoriasis. Both of these events are part of standard clinical practice and are not research-related procedures. Patients who only decline to obtain x-rays won't be excluded from the study.

After completion of the informed consent process, the study site will take photos of the affected fingernails proposed for enrollment.

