- Collection of adverse events, if there are any

The following procedures will be performed at the follow-up visit only:

- Measurements of clear nail growth (in millimeters), clear nail area (in mm²)
- Completion of Nail Psoriasis Severity Index.
- Take pictures of subject's nails
- Collection of survey to document subject's changes in quality of life since the beginning of the study intervention and subjective assessment of nail since the beginning of the study intervention

ADVERSE EVENTS AND REPORTING

Adverse event/effect (AE) assessment will be ongoing throughout the study. All adverse events shall be reported by the clinical Investigator to the Sponsor and IRB following WCMC's reporting policies.

Unanticipated Adverse Effect (UAE)

An unanticipated adverse effect is an adverse effect on health and safety caused by, or associated with, the study intervention, if that problem was not previously identified in nature, severity, or degree of incidence in the investigational plan or application, or any other unanticipated problem that relates to the rights, safety, or welfare of subjects.

The Investigator shall be responsible for determination of the causal relationship of all adverse events to the study intervention and/or procedure. The Principal Investigator is responsible for monitoring the safety of the subjects enrolled.

Any adverse events will be reviewed and analyzed by the Principal Investigator as soon as the event occurs and will be documented in the subject's binder. Any unexpected adverse reactions will be reported by telephone to the IRB within 48 hours of observing the event.

No major adverse effects are anticipated during this study; however, we will screen for severe pain (Pain \geq 8/10 on self-reported scale).

The following minor adverse effects are anticipated: cold/burning sensation, minor to moderate pain (Pain \leq 7 on VAS scale), minor swelling (edema), minor hematomas, and temporary erythema (redness). We will screen for additional possible but not expected adverse effects. If the minute treatment reaches an intolerable threshold of pain $>$ 7, the study intervention will be stopped and more anesthetic may be applied if appropriate. Such pain could result from local injection of the skin. A physician will be on site for the to assess for adverse events as needed.

POTENTIAL ADVERSE EFFECTS:	
Epidermal/Nail Response Assessed	Grading
Pain	0 = none 1 2 3 = extreme
Persistent Erythema	0 = none 1 2 3 = extreme

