Skin atrophy	0 = none 1 2 3 = extreme
Bleeding	0 = none 1 2 3 = extreme
Burning/cold sensation	0 = none 1 2 3 = extreme
Hematoma	0 = none 1 2 3 = extreme

Other (please describe and grade, or enter '0' for none)	
--	--

Table 1. The physician shall evaluate the patient's response to the treatment and screen for possible side effects as listed. 0 = none, 1 = mild, 2 = moderate and 3 = extreme.

Photos shall be taken of any visible treatment effects.

EFFICACY EVALUATIONS

The primary endpoint of this study is to assess the lowest effective concentration of intralesional triamcinolone acetonide in the treatment of nail psoriasis. Safety and tolerability shall be determined based on the reported number of adverse events as outlined in the Adverse Events Section and subject-reported symptoms (if any).

In order to evaluate the efficacy of the proposed treatment, high quality photographs will be taken before and after treatment using standardized lighting, exposure settings, and subject positioning. Trained individuals shall assess the changes in the photographs as outlined in the following paragraphs.

Preliminary assessment of the efficacy of the study intervention will be determined by measuring the amount of clear nail growth. This growth will be compared to the initial amount of clear nail recorded at baseline. Changes in clear area and NaPSI will also be reviewed as study intervention progresses and compared to baseline values.

INSTITUTIONAL REVIEW BOARD

Prior to beginning this study, approval for all study related documents (protocol, consent form, advertising) will be obtained from the Weill Cornell Medical College IRB.

DATA ANALYSIS

Efficacy will be evaluated using nail plate measurements to assess clear nail plate growth and rates of clinical improvement. Clinical improvement will be assessed using the NaPSI, an objective validated measuring tool developed by one of the leaders in the field of nail pathology for use in clinical trials on treatment of nail psoriasis.

Adverse effect intensity will be assessed at each of the treatment visits using a 0-3 scale (0=none, 1=mild, 2=moderate, 3=severe) for each side effect with changes from baseline analyzed using the Wilcoxon signed-ranks test and presented as medians and ranges.

Statistical analysis will be performed using SAS version 9.2 (SAS Institute, Cary, NC). Two-tailed $P < 0.05$ will be considered statistically significant.

MONITORING AND QUALITY ASSURANCE

Site Monitoring

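### The only named side-effect test compares grades with baseline: it yields no rate by concentration and no contrast with saline, and nothing ties a grade to a nail

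*Combined protocol and SAP*

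**What the plan says.** All references are to the combined protocol and SAP.

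- **Objectives:** "Another secondary objective is to determine the rate and nature of side effects experienced by patients using different concentrations of intralesional triamcinolone acetonide".
- **Research Design / Methods, hypothesis:** "The lowest concentration of ITA tested offers the best ratio of efficacy to safety".
- **Data Analysis:** "Adverse effect intensity will be assessed at each of the treatment visits using a 0-3 scale", and the grades are then handled "for each side effect with changes from baseline analyzed using the Wilcoxon signed-ranks test and presented as medians and ranges". Significance is two-sided at 0.05. No grouping is given.
- **Efficacy Evaluations:** "Safety and tolerability shall be determined based on the reported number of adverse events as outlined in the Adverse Events Section". Again no grouping is given.
- **Unit of treatment:** Enrollment and Randomization assigns fingernails, not participants, to four concentrations or saline. The Introduction adds that "a participant with five affected fingernails may have a different concentration of ITA used as the study intervention in each fingernail".
- **Unit of grading:** The caption of the side-effect form in Adverse Events and Reporting reads "The physician shall evaluate the patient's response to the treatment and screen for possible side effects as listed". The form's column heading refers to an epidermal or nail response. Nothing links a grade to a particular nail.
- **Timing:** Adverse Events and Reporting says "Adverse event/effect (AE) assessment will be ongoing throughout the study". The visit lists under Procedures mention adverse event collection after the first treatment visit and at follow-up, but not at the first visit. No section defines the baseline grade.

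**The concern.** The objective and the hypothesis both need side-effect frequency by concentration, with saline as the reference. The named test answers a different question, namely whether grades move after injection. A significant result can arise when every group, saline included, is affected equally. A non-significant result in a small group could be misread as safety. Medians and ranges of a 0-3 grade are not rates.

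The second risk lies in the data. An analysis can be rewritten after the trial, but nail-level grades that were never recorded cannot be recreated. If the form is completed once per participant, a pain or burning grade from someone with saline and several concentrations belongs to no group.

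The undefined baseline matters mainly for pain, because the protocol's Significance section says that nail psoriasis itself is painful.

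**Working it through.** The plan gives no side-effect rate, power or error figure, so there is nothing to reproduce. The check compares what is asked with what is specified, then illustrates how the named test behaves.

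**1. Asked against specified.** Objectives ask for side effects by concentration. Data Analysis gives a within-unit test against baseline, with medians and ranges. Efficacy Evaluations gives an event count without groups. No other section supplies a table or contrast by concentration.

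**2. Could the design support such a table?** The randomization table has 50 entries, 10 for each of the five groups. About 10 nails per group would be available if 50 nails are enrolled and grades are held per nail.

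**3. When is the test significant?** Assumptions, none fixed by the plan: exact test, baseline grades all zero, all changes upward, independent nails. With k affected nails, two-sided P = 2 × 0.5^k.

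- k = 5: 2 × 0.03125 = 0.0625
- k = 6: 2 × 0.015625 = 0.031

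At least six affected nails are therefore needed, and the probability of significance is P(X ≥ 6) for X binomial(n, p). The plan does not say whether the test is pooled or run by group, so both are shown, with the same true rate in all five groups:

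| True rate in every group | Pooled, n = 50 | One group, n = 10 |
|---|---|---|
| 20% | 0.952 | 0.006 |
| 30% | 0.999 | 0.047 |

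There is no dose effect in any row. Pooled, the test is almost always significant. Run by group, it usually is not, although up to 30% of nails are affected. Neither outcome says anything about concentration.

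**4. What can 10 nails per group show?** With 0 of 10 affected, the exact 95% upper limit is 1 − 0.025^(1/10) = 30.8%. With 3 of 10, the exact 95% interval is 6.7% to 65.2%. The intervals are wide, and treating nails as independent ignores correlation within participants.

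**5. Would a dose-ordered test do better?** A within-participant permutation trend test was simulated with 10 participants, independent nails, and saline plus randomly chosen distinct concentrations in each. That is a simplification of how the randomization table assigns nails. Approximate power for a linear 30-point rise from saline to the highest concentration:

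| Affected nails per participant | 0% on saline | 20% on saline |
|---|---|---|
| Five | 51% | 31% |
| Mix of two to five | 34% | 23% |
| Three | 28% | 20% |
| Two | under 1% | 3% |

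Such a test can only be exploratory.

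**The case against.** The strongest reply is that the pieces are already there. Nails are assigned to groups, the form's heading points to a local assessment, most listed effects are local, and adverse events are counted. An analyst could split the results by group, and with 10 participants little formal comparison is possible anyway.

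Much of this stands. Per-nail grading is a natural reading, and a reader who inferred that the plan grades patients only, or that safety by concentration is impossible, would go beyond the text. The unit is ambiguous. Photographs of visible treatment effects are required, so erythema, atrophy or hematoma might be partly recovered by nail. Pain and burning could not. But the split works only if grades are recorded by nail, and the plan specifies neither the recording nor the split.

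The small size is also a fair point. It argues for rates with intervals, not for a test of another question. The calculations above are illustrations under assumed rates, and significance against baseline is not in itself an error when grades truly rise.

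Two other inferences are not supported. One is that side effects go unassessed at the first treatment visit: Data Analysis and the adverse event section both imply that they are assessed, and the Procedures list only omits them. The other is that saline nails receive no lidocaine, so that a pain contrast with saline is confounded. Lidocaine is described with the triamcinolone injection and the placebo is called normal saline, but the protocol also says that other procedures are the same across groups and that only the triamcinolone concentration differs. This is a point to reconcile, not an established confounder.

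**Conclusion.** The point holds. Followed as written, the plan produces no side-effect rate by concentration and no contrast with saline, so a secondary objective and the safety half of the hypothesis are left without an analysis. This rests on the text alone and needs no assumption. The 95% figure for the pooled test does rest on assumptions: 50 nails, a 20% rate everywhere, zero baseline grades, all changes upward and independent nails.

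The possible loss of data is conditional. It arises only if grades are kept per patient, and then mainly for pain and burning in participants who receive several concentrations. The change is worth making before data are collected, because the recording part cannot be repaired afterwards.

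**What to change.** 1. **Recording.** Record each side-effect grade and each local adverse event by nail and assigned group, at every treatment visit including the first and at follow-up. Add a pre-injection pain grade at each treatment visit. Align the first-visit list under Procedures with Data Analysis.
2. **Main safety output.** Specify a table for saline and each concentration giving the number and percentage of nails by worst grade (for pain, the largest rise from the pre-injection grade) and adverse event counts. Give 95% intervals labelled descriptive, because nails within a participant are correlated. Report systemic events per participant, since they cannot be assigned to one concentration.
3. **Signed-rank test.** If it is kept, state that it is not used to judge differences between concentrations and that non-significance is not evidence of safety.
4. **Optional comparison.** A dose-ordered comparison stratified by participant may be added as exploratory, with its low power stated. Power is likely to be lower still if saline nails are also affected.
5. **Lidocaine.** Reconcile Enrollment and Randomization with Procedures on whether the saline injection contains lidocaine, so that pain and burning on saline nails can be interpreted.

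**Cost.** There are more grades per visit. For a participant with five nails, the six named side effects give 5 × 6 = 30 grades, against 6 if the form is meant to be completed once per participant, plus 5 pre-injection pain grades. The analysis work grows slightly. No extra patients or visits are needed.

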patient compliance. The medications must be applied up to two times a day for as long as 2-12 months. Another limitation is limited penetration into the affected part of the nail unit. The therapies are not effective on all nail changes associated with nail psoriasis, and may have poor absorption into the parts of the nail unit responsible for different features of the disease. Systemic therapies such as acitretin, cyclosporin A, and methotrexate are also sometimes used. Good results have been reported with the use of systemics, though they also require strict patient compliance. Biologic drugs such as alefacept, etanercept, infliximab are newer therapies in the treatment of nail psoriasis. They too, have shown to be effective, though confer a risk of severe immunosuppression.

Intralesional corticosteroids, most commonly triamcinolone acetonide (ITA), are often used in the treatment of nail psoriasis. TA is a corticosteroid that is FDA approved for the treatment of psoriasis via intralesional injection. Corticosteroids are used in the treatment of many inflammatory dermatologic diseases. Briefly, they work by inhibiting the body's inflammatory response. At higher doses, the response is more inhibited.

ITA is used in concentrations ranging from 2.5mg/mL - 10mg/mL in the treatment of nail psoriasis.[1, 3] There is debate in the literature regarding the ideal concentration of ITA to treat nail psoriasis.[1] That is, the dose that gives the best efficacy while limiting side effects. No randomized prospective studies investigating this question exist. A number of authors have conducted studies on the efficacy of ITA in the treatment of nail psoriasis using specific concentrations of ITA (most commonly 5mg/mL or 10mg/mL). [6-10] To our knowledge, no authors have directly compared the concentrations to one another. Determining the lowest effective concentration of ITA is important because patients receiving higher than necessary concentrations may experience an increase in side effects. The side effects of corticosteroids such as TA are numerous, and include thinning of the skin at the site of injection, thinning along the lymphatic vessels draining the injection site, allergic reactions, infection, and pituitary suppression.[11]

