Washout Period: Subjects who are using any form of treatment on their nails at the time of the screening visit may participate in the study provided that they are willing to undergo a two-month washout period. During this time, they must abstain from using any nail treatments (including, but not limited to: spa nail treatments, nail polish use, prescribed topical or systemic medications indicated for the nails, over the counter nail treatments, or any other nail intervention with the exception of routine clipping and washing.) After the washout period, the subject may be re-evaluated for participation in the study.

Enrollment and Randomization: Patients with at least two affected fingernails will be enrolled. For each participant, one fingernail will receive an intralesional injection of 0.1-0.2 mL of normal saline (placebo). The other affected fingernail(s) will receive an injection of 0.1-0.2mL of a pre-determined concentration of ITA. Four concentrations of ITA will correspond to four study groups: 2.5mg/mL, 5mg/mL, 7.5mg/mL and 10mg/mL. Participants' fingernails will be randomized such that there are approximately equal numbers of fingernails in each of the five groups (four study interventions, one placebo). To avoid bias, fingernails will be assigned to groups systematically. Fingernails will be assigned to groups in order of anatomical convention. For example, if the subject has involvement of both the thumb, forefinger and third finger of the right hand, the thumb is the first digit, so, if involved, it will be assigned first according to the table below. If a subject has involvement of fingernails of both the right and left hand, the fingernails of the right hand will be assigned before the left. The table assumes that up to 50 nails will be affected between the 10 subjects enrolled. In our clinical experience, this is a reasonable expectation. If more or fewer fingernails are involved during the enrollment period, the randomization table will be adjusted accordingly. The concentration of ITA injected will be different for each group. All other study procedures will be the same between groups.

Fingernail	Group
1	5
2	3
3	4
4	1
5	2
6	4
7	5
8	1
9	3
10	2
11	3
12	4
13	5
14	1
15	2

16	2
17	1
18	3
19	5
20	4
21	5
22	4
23	3
24	2
25	1
26	1
27	2
28	3
29	4
30	5
31	1
32	2
33	4
34	3
35	5
36	5
37	3
38	4
39	2
40	1
41	1
42	3
43	4
44	2
45	5
46	1
47	5
48	2
49	4
50	3

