Table 1: Randomization of subjects' fingernails to groups. Groups are numbered 1-5 and correspond to concentrations of ITA such that 1=2.5mg/mL; 2=5.0mg/mL; 3=7.5mg/mL; 4=10.0mg/mL; 5=placebo.

Procedures: Injections of ITA will be administered using standard methods. Hand hygiene procedures will be performed and the administrator will use gloves. Triamcinolone acetonide, at the determined dose, will be drawn into a solution of 1% lidocaine. The nail fold of the affected nail will be cleaned with an alcohol swab. In addition to the local anesthetic given as part of the injection, the area will be anesthetized with an ethyl chloride spray immediately prior to injection using a 30 gauge needle. During injection, the participant may experience light pressure. Following injection, the wound will be covered with a bandage. A board-certified dermatologist will perform all procedures and will be present to monitor for unlikely adverse events, such as excessive bleeding.

None of these procedures differ from the current standard of care. The only aspect that will differ in the treatment of affected nails is the concentration of ITA used. However, there is no current standard of care regarding the concentration; all concentrations under investigation are part of typical clinical practice and have been validated in studies.[1] The purpose of this study is to determine the lowest effective concentration of ITA in the treatment of nail psoriasis.

The schedule of treatments is as follows:

Treatment will be performed using ITA with a frequency of once per 6 weeks +/- 1 week. A follow-up visit will be performed at 24 weeks, ending the study period.

The following will be performed at the first visit:

- Completion of Nail Psoriasis Severity Index
- Collection of survey to document subject's quality of life
- Use the study intervention (intralesional triamcinolone acetonide injections) on the subject's fingernail(s)
- Take pictures of subject's nails before and possibly after treatment
- Take an X-ray of the affected hand

The following procedures will be performed at every treatment visit after the first, and at the follow-up visit:

- Measurements of clear nail growth (in millimeters), clear nail area (in mm²)
- Completion of Nail Psoriasis Severity Index.
- Use the study intervention (intralesional triamcinolone acetonide injections) on the subject's fingernail(s)
- Take pictures of subject's nails before and possibly after treatment

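### The stated analysis of graded side effects gives neither a rate nor a comparison of concentrations, although a secondary objective asks for side-effect rates at different concentrations

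*Combined protocol and SAP*

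**What the plan says.** Objectives lists, as a secondary aim, to "determine the rate and nature of side effects experienced by patients using different concentrations of intralesional triamcinolone acetonide". Introduction/Background explains why this matters: "patients receiving higher than necessary concentrations may experience an increase in side effects". The first side effect it lists is "thinning of the skin at the site of injection". The hypothesis in Research Design / Methods is "The lowest concentration of ITA tested offers the best ratio of efficacy to safety".

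Adverse Events and Reporting contains a form with six named effects and a line for others, each graded 0 to 3. Its heading mentions the nail, but its caption speaks of how the patient responded, and it shows no field for nail or concentration. Data Analysis then gives one method for these grades: "for each side effect with changes from baseline analyzed using the Wilcoxon signed-ranks test and presented as medians and ranges". No group is named in that sentence.

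Two other statements bear on frequency. Efficacy Evaluations bases safety and tolerability on how many adverse events are reported. Early Termination refers to a rate of unanticipated adverse events, for deciding whether to stop the trial. Neither is split by concentration or tied to an analysis.

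**The concern.** The objective asks how often side effects occur at each concentration. The stated method asks whether grades rose after injection. These are different questions, and the second can be answered in full while the first stays open.

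The recording adds to the difficulty. The Introduction/Background says that a participant with five affected fingernails may have a different concentration in each. If the form is completed once per participant, a grade cannot afterwards be attributed to a dose, and no later analysis can recover it.

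At stake is the safety side of the choice of dose. The case for a low concentration rests partly on fewer side effects, and the plan does not say how that will be shown.

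**Working it through.** The documents give no expected side-effect rates and no power or sample-size calculation, so there is no planned figure to reproduce. The check asks what the stated method returns for known patterns of side effects.

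**Inputs.** Enrollment and Randomization aims for "approximately equal numbers of fingernails in each of the five groups". Counting the randomization table gives 50 nails, 10 in each of groups 1 to 5. The significance level is two-sided 0.05 (Data Analysis). Assumed: baseline grade 0, one post-treatment grade per nail, exact tests, and nails treated as independent.

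**Formula.** With zero differences dropped and k nails that all rise, the exact two-sided signed-rank p is 2/2^k, capped at 1.

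**Mild grade (0 to 1) in k of 10 nails of one group:**

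| k | Rate | Median, range | Signed-rank p |
|---|---|---|---|
| 1 | 10% | 0, 0–1 | 1.0 |
| 2 | 20% | 0, 0–1 | 0.5 |
| 3 | 30% | 0, 0–1 | 0.25 |
| 4 | 40% | 0, 0–1 | 0.125 |
| 5 | 50% | 0.5, 0–1 | 0.0625 |
| 6 | 60% | 1, 0–1 | 0.031 |

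Rates from 10% to 40% share one summary, and none reaches significance.

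**Severe grade.** For pain, suppose 1 nail is at grade 3 and the other 9 are at grade 1, or 4 are at grade 3 and the other 6 at grade 1. Both give median 1, range 1–3, and p = 2/2^10 = 0.002.

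**Comparing verdicts between groups.** 5/10 is not significant (p = 0.0625) and 6/10 is (p = 0.031). Fisher's exact test of 5/10 against 6/10 gives p = 1.0. Reading one dose as harmful and the other as not would rest on a difference for which there is no evidence.

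**Sensitivity to the form of the test.** With an uncorrected normal approximation, the smallest number of equally graded nails that reaches significance is 4 of 10 (p = 0.0455) instead of 6. The threshold moves, but the test remains before against after within a group.

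**What a rate table would show.** Clopper-Pearson 95% intervals: 0/10, 0 to 30.8%; 1/10, 0.3 to 44.5%; 4/10, 12.2 to 73.8%; 8/10, 44.4 to 97.5%. Fisher's test of 1/10 against 4/10 gives p = 0.30; 0/10 against 8/10 gives p = 0.0007.

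**The case against.** The strongest reply is that the signed-rank sentence concerns intensity, while frequency is covered by the count of reported adverse events. That is partly right. Split by group, the count would show differences in frequency. A reader might therefore infer that the safety half of the hypothesis is left wholly unaddressed; the documents do not support that. What is missing is the denominator, the split by concentration and a link between grade and nail.

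A reader might also infer that grades will be pooled over all nails. Then 8 of 50 nails with mild atrophy would give median 0, range 0–1, p = 2/2^8 = 0.0078, whether all 8 were at 10 mg/mL (80% of that group) or 2 were in each triamcinolone group (20%). The text does not say that grades are pooled, and in a five-group design a by-group summary is the more natural reading. The point does not depend on pooling.

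It is also fair that by-group medians set the doses side by side, and that some patterns would separate them. Five nails at none, four mild and one severe give median 0.5 and p = 0.0625; two none, four mild and four severe give median 1 and p = 0.008. So the summary sometimes reflects a difference in rates. It does not do so reliably, and it never states a rate.

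Finally, 10 nails per group is too few for a formal comparison of moderate differences. That stands. It limits what any table can establish, but it is no reason to leave the rate unreported.

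**Conclusion.** The concern holds as a mismatch between a stated secondary objective and the only stated analysis of the graded side effects. Run as written, that analysis yields neither a rate nor a comparison of concentrations, even when done by group. Rates of 10% and 40% can give identical medians and ranges, and adjacent counts of 5 and 6 of 10 can fall on opposite sides of 0.05 with nothing to distinguish them.

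These sizes rest on illustrative grade patterns, a baseline grade of 0, 10 nails per group and, for the p-values, exact tests. That the test compares no concentrations does not rest on them. The change should be made: the objective supports the choice of dose, and per-nail attribution is lost if it is not recorded at the visit.

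**What to change.** 1. Grade each listed side effect per nail at each visit, and record the nail's allocated group. Add swelling, which Adverse Events and Reporting anticipates but the form does not name. Record the 0–10 pain score per nail as well.
2. In Data Analysis, add a table by concentration and placebo giving the number and percent of treated nails with each side effect at any visit, and with a severe grade or pain of 8 or more. Give 95% intervals, labelled descriptive because nails are clustered within 10 participants and simple exact intervals ignore this.
3. State that this table, not the signed-rank p-values, describes side effects by concentration. The signed-rank test may stay as a within-group summary of intensity.

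**Cost.** No added participants, visits or procedures. If the form is now completed once per participant, the new work is grading about seven items, plus swelling, per nail per visit. With 50 nails and injections at weeks 0, 6, 12 and 18, that is 50 × 4 = 200 nail-visits, or 50 × 5 = 250 if the 24-week visit is also graded. The table will not establish moderate differences: 1/10 against 4/10 gives Fisher p = 0.30.
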